# Background

Prostate cancer constitutes about 15 % of new cases of cancer among men globally. Early diagnosis of prostate cancer is associated with significantly better treatment outcome and reduced prostate specific mortality [1]. There are usually no clinical manifestations of prostate cancer until the disease is more advanced, which means that prostate cancer can only be detected early by screening with blood markers such as PSA (prostate specific antigen) or by imaging with Magnetic Resonance Imaging (MRI).

Results from the European Randomized Study of Screening for Prostate Cancer (ERSPC) showed that PSA screening was associated with a 21% relative reduction in the risk of dying from prostate cancer at a median follow-up of 11 years [2].

Prostate cancer screening typically begins with a PSA test. If the PSA is elevated, commonly defined as PSA  $\geq$ 3 ng/ml, the man is usually referred for further investigation with magnetic resonance imaging (MRI). If the MRI shows abnormalities, i.e. PIRADS  $\geq$  3, the man should undergo a prostate biopsy followed by pathological evaluation of the biopsy specimen. The pathologist assigns a Grade Group to the biopsy sample. If the Grade Group is  $\geq$  2 the man is diagnosed with clinically significant prostate cancer (csPC) and should receive appropriate treatment if possible.

PSA testing is controversial due to its low specificity and association with benign prostatic hypertrophy seen in 50% of men aged 50-60 and 80% in men over 70 years [3]. As a result, several adjunct diagnostic tests have been developed to improve detection of csPC and enhance performance of prostate cancer testing. Examples of these tests include 4K Score (OPKO Health Inc.), phi (Beckman Coulter), and Stockholm3 (A3P Biomedical AB). Many of these tests have shown promising results in reducing unnecessary follow-up procedures, such as MRIs and biopsies.

PSA testing is also missing lethal cancers below traditional thresholds (≥ 3 ng/ml), where contemporary evidence now supports a 'U' shaped PSA distribution for csPC with many men harbouring lethal cancer at lower PSA [4]. Some biomarkers, like Stockholm3, have shown potential for earlier detection of csPC particularly in men with low PSA values who might not otherwise be identified. However, despite these advances, none of the adjunct tests are currently recommended in clinical guidelines due to the absence of high-quality randomized studies confirming their clinical utility compared to current standard of care.

Stockholm3 is a multiparametric blood test combining protein-, genetic and clinical markers to predict the risk of csPC. Studies have shown that Stockholm3 can improve prostate cancer detection if it is used as an adjunct test to PSA  $\geq$ 1.5 ng/ml [5-7]. Earlier studies have shown that Stockholm3 as a reflex to PSA  $\geq$  1.5 ng/ml increases the detection of csPC by  $\geq$  20% vs

PSA in a controlled clinical trial [5] and that Stockholm3 as a reflex to PSA 1.5 ng/ml increases the detection of csPC by  $\geq$  40% vs PSA in a clinical utility setting [6].

Both PSA and Stockholm3 are currently used as part of clinical practice in Sweden. PSA testing is available through various laboratories, including Karolinska University Laboratory, Akademiska Sjukhuset, and Unilabs. Stockholm3 is available through Unilabs.

# **Study Objectives**

The main objective of this randomized study is to evaluate the diagnostics performance of standard of care for prostate cancer testing using PSA (control arm) vs an experimental arm using Stockholm3 as a reflex if PSA  $\geq$  1.5 ng/ml in routine clinical care in a primary care setting in Sweden.

# **Primary endpoint measures**

• Number of csPC, defined as Grade Group ≥ 2

#### **Secondary endpoints measures**

- Investigator compliance with diagnostic test outcome, e.g. if the ratio of men with PSA ≥ 3 ng/ml or Stockholm3 ≥11 referred to MRI or biopsy for further testing
- Number of MRIs performed
- Outcome in MRI, i.e. PI-RADS score
- Number of biopsies performed
- Number of benign biopsies
- Number of Grade Group 1 cancers
- Number of Grade Group ≥ 3 cancers
- Prostate cancer deaths
- Deaths due to any cause

# Study design

This is a prospective, multicenter, randomized clinical trial where clinical utility and diagnostic test performance of PSA and Stockholm3 will be evaluated in two phases, Phase I and Phase II.

#### Phase I design

Phase I will compare the clinical utility of using PSA based diagnostics versus using Stockholm3 as a reflex to PSA ≥ 1.5 ng/ml. Participating primary care units will be 1:1 cluster

randomized between control arm with standard of care (SOC) with PSA or experimental arm with Stockholm3 as a reflex to PSA  $\geq$  1.5 ng/ml. Cluster randomization was chosen for this study phase to prevent potential contamination between intervention and control groups. Individual randomization could lead to participants in the control arm unintentionally receiving components of the intervention through interactions with participants in the intervention group. We hypothesize that the use of Stockholm3 improves both test characteristics and the operational structure in the healthcare system (e.g. compliance with test recommendations) compared with today's standard of care. While the effect of better test characteristics is possible to study using individual randomization (see Phase II), the improved operational structure requires cluster randomization to avoid spill-over effects. By randomizing at the cluster level, we thus ensure clearer separation between treatment arms to study the *combined* effect of test characteristics and operations.

This study phase is unblinded for both investigators and participants. Participating primary care units will be cluster-randomized at the study start to either the control or experimental arm. Primary care physicians will recruit men they consider eligible for prostate cancer testing, following standard clinical practice. The decision to refer participants for specialist evaluation, including MRI and biopsy, will be made by the primary care physician in accordance with standard clinical practice

**Primary Care** Primary Care Specialist care Laboratory Control Arm Analysis Recruitment sampling of PSA on referral Eligible and Sampling of Decision on referral at consenting participants in the doctor's Decision primary care discretion R Workup on workup No previous PC Blood Analysis Decision Recruitment Stockholm3 if sampling on referral of PSA Experimental PSA ≥ 1.5-ng/ml Eligible and Primary outcome Sampling of Decision on # csPC consenting referral at Stockholm3 the doctor's participants in primary care discretion Secondary outcome # MRI, # Biopsies, # cnsPC, No previous PC # Benign, Compliance

Figure 1: Phase I design overview

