# **Data Collection**

		Phase I		Phase II	
Data collected	Sample space	Control	Experiment	Control	Experiment
Age	Integer	Х	Х	Х	Х
Family history of prostate cancer	Yes No Not known		Х	Х	Х
Use of 5-alfa reductase inhibitors	Yes No Not known		Х	Х	Х
Earlier negative biopsy conducted with the last 12 months	Yes No Not known		Х	Х	Х
Date of blood sampling	Date format	Х	Х	Х	Х
Date of test result report	Date format	Х	Х	Х	Х
Stockholm3 Risk Score	Integer [1-99]		Х		Х
PSA value	Float [0-9,999]	Х	Х	Х	Х
Digital Rectal Examination	Positive Negative Not known	Х	Х	Х	Х
MRI conducted*	Yes No	Х	Х	Х	Х
Date of MRI (only if MRI conducted)	Date format	Х	Х	Х	Х
PIRADS (only if MRI conducted)	1 2 3 4 5	Х	Х	х	Х
Prostate volume and other data from MRI report (only if MRI conducted)	Text	Х	Х	Х	Х
Biopsy conducted*	Yes No	Х	Х	Х	х
Date of biopsy (only if biopsy conducted)	Date format	Х	Х	Х	Х
ISUP (only if biopsy conducted)	Benign 1 2 3 4 5	х	Х	х	х
Percentage Gleason Score 4 (only if positive	Percentage	Х	Х	Х	Х

		Phase I		Phase II	
Data collected	Sample space	Control	Experiment	Control	Experiment
biopsy conducted)					
Cancer length (only if positive biopsy conducted)	Float [0-999]	Х	X	X	X
Type of biopsy (only if biopsy conducted)	Text	Х	Х	Х	Х
Type of instrument (only if biopsy conducted)	Text	Х	Х	Х	Х
Date of PAD report (only if biopsy conducted)	Date format	Х	Х	Х	Х

Results of MRI and biopsy will be followed up at 4 months after blood test to allow for lag in radiology/pathology.

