## **Step 5: Data collection**

Data will be collected prospectively by medical record analyses to see if the man was referred to MRI and/or prostate biopsy, and if so, the results from these procedures (Grade Group and PIRADS) will be collected. Unilabs will provide a list of all PSA tests at participating primary care units. Data on percentage of Gleason Grade 4, mm cancer, type of biopsy, instrument used will be collected from analyses of pathology reports. Data on type of MRI protocol and MRI instruments will be collected from analysis of radiation reports.

Karolinska Institutet will enter data into a study database and evaluate the results.

MRI and biopsies performed within 4 months from test results delivered to physician will be included in the analysis.

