# Secondary outcomes:

- A generalized linear mixed model (GLMM) with a log-link function and binomial distribution to test for differences in compliance
- Descriptive statistics for MRI and biopsy rates
- Detection of clinically significant prostate cancer at different PSA ranges
- Operating characteristics of PSA and Stockholm3 to predict csPC at different PSA and Stockholm3 cut-offs
- Operating characteristics of PSA and Stockholm3 to predict abnormal MRI (defined as PIRADS ≥3) at different PSA and Stockholm3 cut-offs
- Operating characteristics of PSA and Stockholm3 to predict abnormal MRI (defined as MRI that led to csPC) at different PSA and Stockholm3 cut-offs
- Unnecessary biopsies/MRIs: a normal MRI based on prostate imaging reporting and data system (PIRADS) (I.e. PIRADS 1, 2 and without lesion), benign pathology on biopsy, or low grade ISUP 1 cancer (aka, Grade Group 1, Gleason Score 3+3, Gleason Score 6)
- Adjusted analyses based on potential confounders (e.g., age, PSA levels)
- Healthcare utilization of resources (#MRI, #Biopsy, #ISUP grade group 1 cancers detected)

Randomization stratification factors will be included as covariates in the regression models used for analysis. Data analysis will be performed by the PI or key research personnel. An independent Data Analysis Committee headed by [name] will be overseeing the data analysis.

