#### Data structure

The tables below lay out the general data structure. Data may be structured in the following format but will not be limited to this structure.

Table 1: Clinical characteristics and outcomes

Clinical characteristics	All (N =)	Standard Arm	Experimental arm
Age, years (median, IQR)			
PSA (ng/ml) (median, IQR)			
DRE abnormal (N, %)			
Family history of prostate cancer (N, %)			
Previous negative prostate biopsy (N, %)			
Stockholm3 (median, IQR)			
Underwent MRI (N, %)			
PIRADS ≥3 (N, %) PIRADS ≥4 (N, %)			
Benign biopsy (N, %)			
ISUP 1 Prostate Cancer (N, %)			
ISUP ≥2 Prostate Cancer (N, %)			
ISUP ≥3 Prostate Cancer (N, %)			

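### In Phase I, physicians who know their unit's arm choose which men to recruit; the resulting case-mix difference can be only partly seen and is not corrected in the primary analysis

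*Protocol*

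**What the plan says.** **Order of events.** The protocol's Phase I design section says: "Participating primary care units will be cluster-randomized at the study start to either the control or experimental arm". On blinding it says: "This study phase is unblinded for both investigators and participants". On who enters it says: "Primary care physicians will recruit men they consider eligible for prostate cancer testing, following standard clinical practice". The inclusion criteria add only an age of at least 40 to the physician's judgement. Under Step 2 of the Phase I project description, the physician orders a different test in each arm, so the arm is known when the man is invited. Men who decline receive standard of care.

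**What is collected.** In the Data Collection table, age, PSA value and digital rectal examination are marked in all four columns. Three rows carry only three marks, with Phase I control blank: "Family history of prostate cancer", use of 5-alpha-reductase inhibitors, and a negative biopsy in the last 12 months. The planned Table 1 under Data structure nevertheless has rows for family history and previous negative biopsy, with a column for the standard arm.

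**What is adjusted for.** The Phase I primary model (Step 6) is a log-binomial mixed model with a random intercept per unit. It adjusts for the randomization strata, namely Care Need Index and annual PSA volume, and has modified Poisson as a backup. Adjustment for confounders, with age and PSA as examples, is listed under secondary outcomes.

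**A possible check.** Step 5 says: "Unilabs will provide a list of all PSA tests at participating primary care units". No use of that list to compare recruited with tested men is described.

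**The concern.** Concealed allocation of units protects the comparison of units. It does not protect the comparison of men if they enter after the arm is known and at someone's discretion. Here the incentive to take part differs by arm. Consent at a control unit leaves a man with the PSA test he would have had anyway, while consent at an experimental unit brings Stockholm3. The Ethical considerations section itself accepts that patients may see missing the experimental test as a disadvantage. Physicians at experimental units might therefore recruit more men with a family history, or more low-risk men who are curious about the test. The direction cannot be predicted.

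The primary endpoint is clinically significant cancer per recruited man. If recruited risk differs between arms, the risk ratio mixes the effect of the pathway with the effect of selection. The two stratification variables describe the unit and cannot correct for who was recruited within it.

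**Working it through.** **1. Reproduce the plan's own figure (Study size and outcome, Phase I).** Inputs: control rate 4%, effect 45% (so 5.8%), m = 100, ICC 0.008, 8,000 men, 5% level. The protocol does not state sidedness; two-sided reproduces its figures.

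- Design effect = 1 + (m − 1) × ICC = 1 + 99 × 0.008 = 1.792.
- Effective men per arm = 4,000 / 1.792 = 2,232.
- Power = 79.6%, against a stated 80%.
- At the ends of the stated range, the same method gives 56.4% (40% effect, m = 150, ICC 0.01) and 91.9% (50% effect, m = 100, ICC 0.005), against 58% and 92%.

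The stated power stands. The same effective size is used below.

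**2. No true effect, but recruited risk differs.** Let p0 = 0.04 and p1 = 0.04 × (1 + d), where d is the relative risk difference due to recruitment alone. With p̄ the mean of the two rates, SE = √(2 p̄(1 − p̄)/2,232), and the chance of a false result in favour of Stockholm3 is 1 − Φ(1.96 − (p1 − p0)/SE).

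| d (assumed) | p1 | (p1 − p0)/SE | Chance of false superiority |
|---|---|---|---|
| 0 | 4.0% | 0 | 2.5% |
| 5% | 4.2% | 0.34 | 5.2% |
| 10% | 4.4% | 0.67 | 9.8% |
| 20% | 4.8% | 1.30 | 25.6% |

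**3. What one uncollected factor could contribute.** If a factor carries relative risk R for clinically significant cancer and has prevalence q0 in control and q1 in the experimental arm, the spurious risk ratio is (1 + q1(R − 1)) / (1 + q0(R − 1)). R and the prevalences are assumptions.

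- R = 1.5, 10% against 15%: 1.075 / 1.05 = 1.024.
- R = 2.5, 10% against 20%: 1.30 / 1.15 = 1.13.

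Put into step 2, these give about 3.6% and 13.6%. A 10% shift is thus within reach of one strong factor; a 20% shift would need several acting together.

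**4. The opposite direction.** Take a true 45% increase with the experimental arm's recruited risk 10% lower. Then p1 = 0.058 × 0.9 = 0.0522 and SE = √((0.04 × 0.96 + 0.0522 × 0.9478)/2,232) = 0.00627. Power = Φ(0.0122/0.00627 − 1.96) ≈ 49%, down from 80%.

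**The case against.** A reader might infer that recruitment bias can be neither seen nor corrected. The protocol does not support that. Age, PSA and digital rectal examination are collected in both Phase I arms and tabulated by arm. A secondary analysis adjusts for age and PSA, and its list of confounders is open-ended. What cannot be seen is imbalance in the three uncollected items. What is uncorrected is the primary estimate.

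Other objections have weight:

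- **The analysis section is a summary.** A statistical analysis plan, not shown here, is promised before study start and may add covariates. It cannot recover control-arm data that the protocol does not collect.
- **Table 1 is a generic layout.** It is reused for Phase II and has a Stockholm3 row that no control arm can fill. Its biopsy item also differs from the collected one (any previous biopsy against the last 12 months). The mismatch needs tidying, but does not show that the baseline plan as a whole is broken.
- **The shift sizes are assumed.** They also describe the total risk difference, part of which would run through age and PSA, which are measured.
- **Open cluster allocation is deliberate.** The protocol wants the combined effect of test and operations and explains why individual randomization cannot give it. That justifies the design, but does not remove the need to measure and adjust for case mix.

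A reader might also extend the point to Phase II. It does not apply there: men are randomized individually at the laboratory, and physicians and men are blinded at sampling.

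**Conclusion.** The concern holds in a limited form and should be acted on. Phase I recruitment takes place after allocation, with the arm known and eligibility largely at the physician's discretion. The check on the resulting case mix is incomplete, and the primary model contains no individual-level covariate.

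Under the protocol's central design assumptions, even a 5% shift in recruited risk doubles the one-directional error, from 2.5% to about 5%. Shifts of 10% and 20% take it to about 10% and 26%. These are illustrations and not forecasts; nothing in the document says how large the shift will be or which way it will run. No stated figure in the sample size section is wrong on this account.

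The finding about uncollected items rests on the Phase I control cells being intentionally blank. The neighbouring rows with four marks, and the fact that the same items are marked for PSA-only men in Phase II, make that the natural reading.

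**What to change.** For Phase I only:

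1. Add age as an individual-level covariate in the primary model, alongside the strata. It is already collected in both arms. Keep the modified Poisson backup for convergence problems.
2. Collect family history, 5-alpha-reductase inhibitor use and earlier negative biopsy in the control arm on the same form as in the experimental arm. Include them in the confounder-adjusted analysis already planned, and give the biopsy item the same definition in the Data Collection table and Table 1.
3. From the Unilabs list, report recruited against all tested men per unit, by arm, as a description only. The protocol does not say whether the list carries age or counts Stockholm3 orders in the same way as PSA orders, and PSA is drawn from different tube types in the two arms. Reweighting recruited men to the list is therefore not proposed.

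The cost is three extra form items for control-arm men and a little more analysis. No additional men are needed. The form change should be in place before enrolment, because these items are best recorded at recruitment.

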## Phase II design

Phase II will compare the diagnostic test performance of Stockholm3 (as a reflex to PSA  $\geq$  1.5 ng/ml) to using PSA only. Participants will be 1:1 randomized between control arm with PSA and experimental arm with Stockholm3 as reflex to PSA  $\geq$  1.5 ng/ml. For Phase II, we are thus interested in comparing the test characteristics in isolation (i.e. not Stockholm3's effect on operations, e.g. compliance) and we therefore use randomization on an individual level.

This study phase includes delayed unblinding, meaning that both investigators and participants will remain blinded at the time of blood sampling and will only be unblinded upon receiving the test results. Primary care physicians will recruit men they consider eligible for prostate cancer testing, following standard clinical practice. All participants will undergo blood sampling for both PSA and Stockholm3. Randomization will be performed at the laboratory, and only the assigned test will be analyzed. Men with PSA  $\geq$  3 ng/mL (standard of care) or Stockholm3  $\geq$  11 will be required to undergo further evaluation with MRI.

**Primary Care** Laboratory Primary Care Specialist care Analysis of PSA Referral to MRI if Blood Decision Recruitment R Workup  $PSA \ge 3 \text{ ng/ml or}$ sampling on workup Stockholm3 ≥ 11 Sampling of blood for both Eligible and Referral decision consenting is mandated if participants in PSA and  $PSA \ge 3 \text{ ng/ml or i}$ Analysis of Stockholm3 primary care Analysis Stockholm3 ≥ 11 Primary outcome Stockholm3 if PSA ≥ 1.5-# csPC No previous PC na/ml Secondary outcome # MRI, # Biopsies, # cnsPC, # Benign, Compliance

Figure 2: Phase II design overview

# Study population

#### **Inclusion criteria**

- Men eligible for prostate cancer testing, as determined by their physician
- Age ≥ 40 years

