#### **Exclusion criteria**

- Previous diagnosis of prostate cancer
- Cognitive disabilities unable to understand study information material

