#### Step 2: Recruitment, consent, and blood sampling

Men with no previous prostate cancer diagnosis, eligible for prostate cancer test according to standard of care and meeting the study inclusion/exclusion criteria, will be offered to participate in the study.

Men that are interested and have read the *Research Participant Information* will sign an informed consent. Men that are not interested to participate in the study will be offered standard of care.

The physician orders PSA (control arm) or Stockholm3 (experimental arm) from Unilabs' catalog. The research participant proceeds to the sampling unit, where blood is collected for PSA (control arm, 1 x serum tube) or Stockholm3 (experimental arm, 2 x EDTA tubes). The samples are transported to Unilabs in Solna/Huvudsta.

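### Phase I neither restricts nor records an earlier PSA or Stockholm3 result, so open-label recruitment after allocation can enrol men with a known raised PSA unequally between arms, with no means of checking it

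*Protocol*

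**What the plan says.** The Inclusion criteria are age 40 or over and "Men eligible for prostate cancer testing, as determined by their physician". The Exclusion criteria are "Previous diagnosis of prostate cancer" and cognitive disability. Neither list refers to an earlier PSA or Stockholm3 result. The Data Collection table has one PSA value and one Stockholm3 score per man, with the dates of blood sampling and of the result report. It has no item for an earlier value or its date. The nearest item is a negative biopsy in the past year.

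On recruitment, the Phase I design section says "Participating primary care units will be cluster-randomized at the study start to either the control or experimental arm", "This study phase is unblinded for both investigators and participants" and "Primary care physicians will recruit men they consider eligible for prostate cancer testing, following standard clinical practice". Step 2 of the Phase I project description adds "The physician orders PSA (control arm) or Stockholm3 (experimental arm) from Unilabs' catalog", and for men who decline, "Men that are not interested to participate in the study will be offered standard of care". The control arm is itself standard care with PSA (Randomization procedure, Phase I).

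Step 5 of Phase I provides that "Unilabs will provide a list of all PSA tests at participating primary care units", but gives no period for that list and no use of it for earlier results. The primary model adjusts for the two unit-level stratification factors. Adjustment for age and PSA appears only under secondary outcomes.

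**The concern.** Take a man whose routine PSA a month ago was 5 ng/ml. At a control unit, study entry gives him another PSA, the same care he would get outside the trial. At an experimental unit, entry gives his physician a new test that bears on the referral decision. Both physicians know their arm before they decide whether to invite him, and the criteria allow either to do so.

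The primary endpoint is counted among enrolled men. If the control unit refers him on the result it already has and does not enrol him, his cancer is still found, but it is not counted in the control arm. If the experimental unit enrols him, it is counted there. The arms would then differ in who is counted and not only in what is detected. This is separate from the operational benefit of Stockholm3 that the Phase I design section sets out to capture through cluster randomization.

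**Working it through.** **The plan's own figure.** From Study size and outcome, Phase I: 8,000 men, 4% in control, a 45% relative increase (5.8%), cluster size m = 100, ICC = 0.008, 5% significance level, taken as two-sided.

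- Design effect = 1 + (100 − 1) × 0.008 = 1.792.
- Effective number per arm = 4,000 / 1.792 ≈ 2,232.
- Power for 4% against 5.8% = 79.6%, which matches the stated 80%.

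**Enrichment of the experimental arm.** Assume that Stockholm3 has no effect, that a share q of experimental men enters because of a known raised PSA, that these men have cancer yield y, that all other men have the planned 4%, and that no such men enter the control arm. The protocol gives neither q nor y; both are assumptions.

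Experimental rate = 4% × (1 − q) + y × q; RR = rate / 4%.

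| q | y | Experimental rate | RR with no true effect |
|---|---|---|---|
| 3% | 20% | 3.88% + 0.60% = 4.48% | 1.12 |
| 5% | 20% | 3.80% + 1.00% = 4.80% | 1.20 |
| 10% | 10% | 3.60% + 1.00% = 4.60% | 1.15 |
| 10% | 20% | 3.60% + 2.00% = 5.60% | 1.40 |
| 10% | 30% | 3.60% + 3.00% = 6.60% | 1.65 |

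Over q of 3–10% and y of 15–25%, the RR runs from 1.08 to 1.53.

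**Chance of a false positive.** With the same effective 2,232 men per arm, the chance of a significant result in favour of Stockholm3 is 26% at q = 5%, y = 20%, and 71% at q = 10%, y = 20%. The nominal chance in that direction is 2.5%.

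**Share needed to reach the central planned RR of 1.45.** q = (5.8% − 4%) / (y − 4%). This gives 30% at y = 10%, 11.25% at y = 20%, and 6.9% at y = 30%.

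**Depletion of the control arm.** Suppose instead that a share g of usual recruits has a known raised PSA with yield y, that experimental units enrol them as usual (rate 4%), and that control units refer them without enrolling them. Control rate = (4% − g × y) / (1 − g). With y = 20%:

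- g = 2%: 3.6% / 0.98 = 3.67%, RR 1.09.
- g = 5%: 3.0% / 0.95 = 3.16%, RR 1.27.
- g = 8%: 2.4% / 0.92 = 2.61%, RR 1.53.

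**The case against.** The protocol nowhere says that control units will refer such men without enrolling them. Referral is at the physician's discretion, so a repeat PSA with enrolment is equally permitted. Step 2 also asks that a man be eligible for testing under standard care, and the Background describes men with PSA of 3 ng/ml or more as usually referred onward, so some of these men may be regarded as past the testing step in both arms. These points stand. They make q smaller and uncertain, but they do not make it equal between arms.

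Enrichment would also be partly visible. The study PSA is recorded in both arms, is to be tabulated by arm, and is used to break down detection by PSA range. At q = 10%, about 400 of 4,000 men would be involved, and most would show a high study PSA. That stands too. But the study PSA cannot separate a man recruited on an earlier high value from one newly found to be high, and the PSA-adjusted analysis is secondary.

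Three stronger readings go beyond the documents:

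- A reader might infer that selection alone will produce the planned effect. It can do so only under particular assumed values, such as q = 10% with y = 20% for the lower planned RR of 1.40. At a yield of 10%, three in ten experimental men would have to enter this way to give 1.45.
- A reader might infer that men with a known PSA below 1.5 ng/ml are selected in the opposite direction. Entry would only repeat a PSA for them in either arm, so no difference follows.
- A reader might infer that the planned 4% describes men not selected on an earlier result. The sample size section does not state its source population.

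Finally, a sensitivity analysis would normally belong to the SAP, which is not at hand. But an SAP can use earlier results only if they are collected, and data items are set in the protocol.

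**Conclusion.** The gap is real and specific to Phase I. Known allocation, open-label recruitment by physician judgement, and a control arm equal to care outside the trial give a plausible route to unequal enrolment of men with a known raised PSA. The primary model, adjusted only for unit-level factors, would not remove the resulting bias. Its direction would favour Stockholm3.

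Its size cannot be determined from the protocol. The RRs of 1.12, 1.20 and 1.40 rest on a 4% base rate, a 20% yield, shares of 3%, 5% and 10%, and no such men in the control arm; partial enrolment there would reduce them. The conclusion is that this bias could occur and could not be properly assessed with the planned data, not that it will occur.

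Phase II is much less exposed, because allocation is individual, takes place at the laboratory, and both parties are blinded at blood sampling.

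**What to change.** 1. Add to the Data Collection table and to Step 5 of Phase I the date and value of each participant's latest PSA and Stockholm3 before the index order. The laboratory would supply these, with a look-back that begins before study start. All units must use this laboratory, and it already lists their PSA tests.
2. Report by arm the share of men with an earlier PSA of 3 ng/ml or more.
3. Pre-specify, as a key sensitivity analysis, the Phase I comparison of detection rates restricted to men with no earlier result in a fixed period before the index order (for example 12 months; the sponsor should set it).

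The cost is one additional data extract and some analysis work. Tests done at other laboratories may be missed, and the restricted analysis will be less precise. Neither step changes the sample size or the men who may enter.

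An entry washout, identical in both arms, is optional. It would narrow the routine-care population that the Study Objectives describe, and it would not end all selective recruitment in an open cluster trial.
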